8.1.2 Efficacy Assessments

For all baseline assessments and follow-up visits, refer to the Schedule of Assessments (SOA) for procedure to be done, and details below for each assessment.

8.1.2.1 Measures of clinical support, limitations and infection control

The subject's clinical status will be captured on each study day while hospitalized and on Day 15 and 29 if hospitalized or the subject returns for an in-person clinic visit. It will also be captured on Day 22 during a phone visit. Clinical status is largely measured by the ordinal scale and the NEWS. Unlike the NEWS, the ordinal scale can also be evaluated over the phone if the discharged subject is unable to return for visits on Day 15 and 29 as well as on Day 22.

Ideally, complete the ordinal scale concurrently with the NEW Score just prior to infusion, as time permits. The following measures are recorded for the ordinal scale:

- Hospitalization.
- Oxygen requirement.
- Non-invasive mechanical ventilation (via mask) requirement.
- High flow oxygen requirement.
- Invasive mechanical ventilation (via endotracheal tube or tracheostomy tube) requirement.
- ECMO requirement.
- Ongoing medical care preventing hospital discharge (COVID-19 related or other medical conditions).
- Limitations of physical activity (self-assessed).
- Isolated for infection control purposes.

8.1.2.2 Ordinal Scale

The ordinal scale is the primary measure of clinical outcome.

The scale used in this study is as follows (from worst to best):

- Death;
- Hospitalized, on invasive mechanical ventilation or ECMO;
- Hospitalized, on non-invasive ventilation or high flow oxygen devices;
- Hospitalized, requiring supplemental oxygen;

- Hospitalized, not requiring supplemental oxygen - requiring ongoing medical care (COVID-19 related or otherwise);
- Hospitalized, not requiring supplemental oxygen - no longer requires ongoing medical care;
 - This would include those kept in hospital for quarantine/infection control, awaiting bed in rehabilitation facility or homecare, etc.
- Not hospitalized, limitation on activities and/or requiring home oxygen;
- Not hospitalized, no limitations on activities

To determine a subject's clinical status using the ordinal scale: On Day 1, report their clinical status at randomization. On Day 2, report the period from randomization to midnight on Day 1. On Day 3 through Day 11, or until discharged, and on Days 15, 22 and 29, provide the worst clinical assessment for the previous day (i.e., midnight to midnight; 00:00 – 23:59 (24-hr clock)). For example, on study Day 3 when completing the form, the worse clinical outcome measure of Day 2 is captured with the worst being death followed by ECMO, mechanical ventilation, etc. The Day 2 measurement is assessed as occurring anytime in that 24-hour period (00:00 to 23:59).

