To evaluate the clinical efficacy, as assessed by time to recovery, of different investigational therapeutics as compared to the control arm.	Day of recovery is defined as the first day on which the subject satisfies one of the following three categories from the ordinal scale: 
 • Hospitalized, not requiring supplemental oxygen - no longer requires ongoing medical care; • Not hospitalized, limitation on activities and/or requiring home oxygen; • Not hospitalized, no limitations on activities. Recovery is evaluated up until Day 29.
Key Secondary	
To evaluate the clinical efficacy of different investigational therapeutics relative to the control arm in adults hospitalized with COVID-19 according to clinical status (8-point ordinal scale) at Day 15	
 • Death; • Hospitalized, on invasive mechanical ventilation or ECMO; • Hospitalized, on non-invasive ventilation or high flow oxygen devices; • Hospitalized, requiring supplemental oxygen; • Hospitalized, not requiring supplemental oxygen - requiring ongoing medical care (COVID-19 related or otherwise); • Hospitalized, not requiring supplemental oxygen - no longer requires ongoing medical care; • Not hospitalized, limitation on activities and/or requiring home oxygen; • Not hospitalized, no limitations on activities.
Additional Secondary	

OBJECTIVES	ENDPOINTS (OUTCOME MEASURES)

1. To evaluate the clinical efficacy of different investigational therapeutics as compared to the control arm as assessed by:
 
 • Clinical Severity 
 ○ Ordinal scale: 
 ▪ Time to an improvement of one category and two categories from Day 1 (baseline) using an ordinal scale. ▪ Subject clinical status using ordinal scale at Days 3, 5, 8, 11, 15, 22, and 29. ▪ Mean change in the ordinal scale from Day 1 to Days 3, 5, 8, 11, 15, 22, and 29. 	
 • Clinical outcome assessed using ordinal scale daily while hospitalized and on Days 15, 22, and 29.

 ○ National Early Warning Score (NEWS): 
 ▪ Time to discharge or to a NEWS of ≤ 2 and maintained for 24 hours, whichever occurs first. ▪ Change from Day 1 to Days 3, 5, 8, 11, 15, and 29 in NEWS. 	
 • NEWS assessed daily while hospitalized and on Days 15 and 29.

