3.3.7. Days of Ventilation/ECMO

Ventilator / ECMO days will be defined as the number of days where the clinical status score is equal to 7. After discharge, the CRF question regarding days of ventilation will be used. The total number of days will be the sum of all reported days, regardless of whether the days occur consecutively or in disjoint intervals. See Section 6.5 for the plan for handling subjects who do not have data through Day 29 or die prior to Day 29.

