4.3. Efficacy and Safety Variables

For each study day while the patient is hospitalized, the clinical status will be recorded on an 8-point ordinal scale as follows:

- Day 1 – The clinical assessment at the time of randomization.
- Day 2 - The most severe assessment occurring at any time between randomization and midnight the day of randomization.
- Day 3+ - The most severe assessment occurring from midnight to midnight (00:00 to 23:59) of the prior day (e.g., the value recorded on Day 3 will be the most severe outcome that occurred on Day 2).

where the clinical status scale is defined as follows:

8. Death;
7. Hospitalized, on invasive mechanical ventilation or ECMO;
6. Hospitalized, on non-invasive ventilation or high flow oxygen devices;
5. Hospitalized, requiring supplemental oxygen;
4. Hospitalized, not requiring supplemental oxygen- requiring ongoing medical care (COVID-19 related or otherwise);
3. Hospitalized, not requiring supplemental oxygen - no longer requires ongoing medical care;

2. Not hospitalized, limitation on activities;
1. Not hospitalized, no limitations on activities

A modified version of the ordinal scale will be used in sensitivity analyses of the primary and secondary outcomes. The modified scale will be as follows:

8. Death;
7. Hospitalized, on invasive mechanical ventilation or ECMO;
6. Hospitalized, on non-invasive ventilation or high flow oxygen devices;
5. Hospitalized, requiring supplemental oxygen;
4. Hospitalized, not requiring supplemental oxygen- requiring ongoing medical care (COVID-19 related or otherwise);
3. Not hospitalized, limitation on activities;
2. Hospitalized, not requiring supplemental oxygen - no longer requires ongoing medical care; or Not hospitalized, no limitations on activities.

That is, category 1 and 3 of the original scale will be combined into the lowest category.

NEWS has demonstrated an ability to discriminate subjects at risk of poor outcomes. This score is based on 7 clinical parameters (see [Table 1](#)). This should be evaluated at the first assessment of a given study day and prior to administration of study product. The 7 parameters can be obtained from the hospital chart using the last measurement prior to the time of assessment and a numeric score given for each parameter (e.g., a RR of 9 is one point, oxygen saturation of 92 is two points). This is recorded for the day obtained. i.e., on Day N, the Day N score is obtained and recorded as the Day N score.

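### Protocol 8.1.2.2, read literally, stops daily ordinal scoring after Day 11 and leaves up to 15 inpatient days unscored, against the daily rule elsewhere in the protocol and SAP

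*Protocol*

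**What the plan says.** Protocol 8.1.2.2 gives the scoring instruction in three steps:

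- Day 1: "On Day 1, report their clinical status at randomization".
- Day 2: "On Day 2, report the period from randomization to midnight on Day 1".
- After that: "On Day 3 through Day 11, or until discharged, and on Days 15, 22 and 29", each form reporting the worst status of the day before.

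The other places that set the frequency say daily:

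- Protocol 8.1.2.1, the subsection just before: "The subject's clinical status will be captured on each study day while hospitalized".
- Protocol 1.1 and Section 3, endpoint tables: "Clinical outcome assessed using ordinal scale daily while hospitalized and on Days 15, 22, and 29".
- Protocol 1.2, Table 1: the clinical data row runs daily until discharge, and footnote 1 names the ordinal score among those data.
- SAP 4.3: "For each study day while the patient is hospitalized, the clinical status will be recorded". Its last step is open-ended from Day 3, with no stop at Day 11.

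The SAP then builds outcomes on these scores. Section 3.3.2 dates recovery by the first assessed day with a score of 1, 2 or 3. Section 3.3.7 states: "Ventilator / ECMO days will be defined as the number of days where the clinical status score is equal to 7". Sections 3.3.6 and 3.3.8 define non-invasive ventilation and oxygen days in the same way.

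**The concern.** Category 3 is recovery in a subject who is still in hospital. It can be seen only through inpatient scores, because the discharge fallback in SAP 3.3.2 does not date it. A day without a score cannot be the recovery day, and it cannot add to a count of days with a given score. SAP 6.5 has imputation rules for loss to follow-up, early termination, missing data after discharge and some readmissions. It has none for an unscored day between two scored inpatient days.

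Category 3 is not a rare state in the plan's own assumptions: the five control scenarios in Protocol Table 5 put 9% to 25% of subjects there at Day 15. (That is occupancy on one day, not the share first reaching category 3 on an unscored day, which the documents do not give.)

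The same mechanism reaches time to one- or two-category improvement (SAP 3.3.4). It also reaches new-support incidence (SAP 8.2.4, 8.2.6, 8.2.8), where an escalation that starts and ends inside a gap would not be seen.

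**Working it through.** The documents give no count of scored or unscored days, so there is no such figure to reproduce. The dating rule can be checked against the SAP's own example: in 3.3.2, a score of 3 recorded on Day 4 gives a time to recovery of 3 days, so assessed day = form day − 1. That rule is used below, with Days 15, 22 and 29 taken at their nominal dates.

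**1. Days scored under 8.1.2.2, stay through Day 29**

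- Form days: 1-11, 15, 22, 29, so 11 + 3 = 14.
- Form days omitted: 12-14 (3), 16-21 (6), 23-28 (6), so 3 + 6 + 6 = 15, and 14 + 15 = 29.
- Distinct assessed days: forms 1 and 2 both describe Day 1, so the list is 1-10, 14, 21, 28, which is 13 of 28. Missing are 11-13, 15-20 and 22-27, again 15.

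Under the daily rule the same subject has 29 form days and 28 assessed days.

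**2. Dating of recovery first reached in hospital**

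Delay = next assessed day on the list − true first day in category 3, for a subject who stays in hospital.

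| True first day | Next assessed day | Delay |
|---|---|---|
| 11, 12, 13 | 14 | 3, 2, 1 |
| 15, 16, 17, 18, 19, 20 | 21 | 6, 5, 4, 3, 2, 1 |
| 22, 23, 24, 25, 26, 27 | 28 | 6, 5, 4, 3, 2, 1 |
| 1-10, 14, 21, 28 | same day | 0 |

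If discharge comes before the next scored day, recovery is dated at discharge and the delay is shorter.

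**3. Score-based day counts, continuous support from Day 1, survivor**

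Share counted = scored days up to the end of support ÷ days of support. SAP 3.3.6 to 3.3.8 do not say whether days are counted by form day or by assessed day, so both are shown.

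| Support to Day | By form day | By assessed day |
|---|---|---|
| 11 | 11/11 = 100% | 10/11 = 91% |
| 14 | 11/14 = 79% | 11/14 = 79% |
| 21 | 12/21 = 57% | 12/21 = 57% |
| 26 | 13/26 = 50% | 12/26 = 46% |
| 28 | 13/28 = 46% | 13/28 = 46% |
| 29 | 14/29 = 48% | 13/28 = 46% |

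The loss therefore reaches about half only for support lasting to about Day 26 or later. A spell lying wholly inside one gap, such as form Days 16-21, would count 0 of 6.

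**4. Outcomes outside this arithmetic**

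- Hospitalization days run from randomization to discharge (SAP 3.3.9) and use no scores.
- Support days in subjects who die are described as imputed to 28 (SAP 8.2.3, 8.2.5, 8.2.7).
- Recovery by discharge is dated at discharge (SAP 3.3.2).

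**The case against.** The best answer is that no site would read the sentence this way. Its main job is to set the look-back period, and frequency is set elsewhere: Protocol 8.1.2 opens by sending sites to the Schedule of Assessments, which says daily, and so does 8.1.2.1. SAP Section 15 records that SAP Section 4 was updated to match protocol version 3.0, and SAP 4.3 came out as daily, which suggests that its authors understood the protocol so. The discharge clause is also ambiguous: if it means that scoring continues until discharge, nothing is omitted.

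Much of this stands. A reader might infer that 8.1.2.2 is the only instruction sites see; it is not, since 8.1.2.1 and the Schedule are equally addressed to them. It does not remove the conflict. The natural reading of the clause is whichever comes first, because a stop at Day 11 has no function if scoring runs to discharge anyway. Day 11 is also a real cut-off elsewhere, for concomitant medication review and for the last inpatient laboratory day before Day 15.

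A reader might also infer that the treatment comparison is biased. The documents do not support that: any gap falls on the same study days in both arms of a blinded trial, and neither a bias nor a loss of power has been shown.

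**Conclusion.** The contradiction is real and concerns how the scale behind the primary endpoint is scored. Its effect is conditional and bounded. It arises only if sites followed 8.1.2.2 literally, and the documents do not show whether they did.

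On that condition:

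- Up to 15 inpatient days go unscored for a stay through Day 29. Earlier discharge omits fewer, and discharge by Day 11 omits none.
- Recovery first reached in hospital on an unscored day is dated up to 3 days late in the first gap and up to 6 in the later two, with discharge as the cap.
- Oxygen, non-invasive ventilation and ventilator/ECMO counts in survivors fall by up to about half for support to about Day 26 or later. For support from baseline ending by Day 11, the loss is nil by form day and at most one day by assessed day.

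A reader might infer that support-day counts are halved in general, or that every unscored day is treated as a day without support. Neither holds. Half is the extreme for long support, subjects who die are set to 28 days, and subjects lost to follow-up while on support are carried as supported through Day 29 (SAP 6.5).

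The figures assume nominal visit days; the windows in the Schedule (±2 days at Day 15, ±3 at Days 22 and 29) would shift them.

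**What to change.** Reconcile Protocol 8.1.2.2 with the Schedule of Assessments and SAP 4.3. One possible wording: *From Day 3, on every day in hospital through Day 29, and after discharge on Days 15, 22 and 29, report the worst status of the preceding calendar day.*

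Before database lock, tabulate by arm the completeness of ordinal scores for subjects still in hospital on Days 12-14, 16-21 and 23-28. If the scores are there, the matter is closed. If gaps appear, add a rule to SAP 6.5 for an unscored day between scored inpatient days, and report how many recovery dates and support-day counts it affects.

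The cost is one protocol sentence and one completeness table. No assessment is added, because the Schedule already requires these data daily.

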8.1.2.3 National Early Warning Score (NEWS)

NEWS has demonstrated an ability to discriminate subjects at risk of poor outcomes. (Smith, 2016). This score is based on 7 clinical parameters (see Table 2). The NEWS is being used as an efficacy measure. The NEWS Score should be evaluated daily while hospitalized and on Days 15 and 29. It can be performed concurrently with the Ordinal Scale. This should be evaluated at a consistent time for each study day and prior to administration of study product. The 7 parameters can be obtained from the hospital chart or electronic medical record (EMR) using the last measurement prior to the time of assessment and a numeric score is given for each parameter (e.g., a RR of 9 is one point, oxygen saturation of 92 is two points). This is recorded for the day obtained (i.e., on Day 3, the vital signs and other parameters from Day 3 are used to obtain NEWS Score for Day 3).

Table 2. National Early Warning Score (NEWS)

PHYSIOLOGICAL PARAMETERS	3	2	1	0	1	2	3
Respiration Rate	≤8		9 - 11	12 - 20		21 - 24	≥25
Oxygen Saturations	≤91	92 - 93	94 - 95	≥96			
Any Supplemental Oxygen		Yes		No			
Temperature	≤35.0		35.1 - 36.0	36.1 - 38.0	38.1 - 39.0	≥39.1	
Systolic BP	≤90	91 - 100	101 - 110	111 - 219			≥220
Heart Rate	≤40		41 - 50	51 - 90	91 - 110	111 - 130	≥131
Level of Consciousness				A			V, P, or U

Level of consciousness = alert (A), and arousable only to voice (V) or pain (P), and unresponsive (U).

8.1.3 Exploratory assessments

8.1.3.1 Viral Load and/or Shedding

As outlined on the SOA, OP swabs and plasma and serum will be collected on Day 1; and Days 3, 5, 8, and 11 (while hospitalized); and OP swabs and serum on Day 15 and 29 (if attends an in-person visit or still hospitalized). Samples are stored as outlined in the MOP. These assays are not developed yet, and the ability to test samples at one central lab is not clear. Therefore, while viral load/shedding is thought to be an important endpoint, considering the limitations above, it is listed as an exploratory endpoint.

OP swabs are preferred, but if these are not obtainable, nasopharyngeal (NP) swabs may be substituted. Due to limited lack of swabs and other supplies at some sites and limitations on personal protective equipment (PPE), the inability to obtain these samples are not considered protocol deviations and should be documented in the subject's record.

If virology assays can be set up with enough numbers of specimens tested, these data will be submitted as part of the Clinical Study Report (CSR). This may be submitted separately, as a supplemental CSR.

Samples collected for viral assessment may be probed for the emergence of antiviral resistance at a future date. These data, if available, may be submitted as a supplement report.

The schedule of assessments (SOA, Section 1.2) lists several research laboratory samples. It is preferred that these samples are collected and sent to the NIAID repository to be tested in one central laboratory. Current US Centers for Disease Control and Prevention (CDC) guidance is these samples can be processed in a Biosafety Laboratory (BSL) 2 environment. However, institutions may impose restrictions on processing the samples (i.e., they may require BSL-3) or there may be restrictions on sending samples. In these circumstances, the following apply:

Blood for PCR SARS-CoV-2

- If the samples can be processed but cannot be sent to the repository, the samples may be stored locally.
- The sponsor may elect to have some or all of these samples run locally, pending confirmation of the assays to be used and the qualifications of the local laboratory. The sponsor will work with the site to determine when this could occur and how these data can be imported into the study database.
- If a BSL-3 environment is needed for processing these samples, these samples may be omitted.

Oropharyngeal swab

- If the samples can be processed but cannot be sent to the repository, the samples may be stored locally.
- The sponsor may elect to have some or all of these samples run locally, pending confirmation of the assays to be used and the qualifications of the local laboratory. The sponsor will work with the site to determine when this could occur and how these data can be imported into the study database.
- If a BSL-3 environment is needed for processing these samples, these samples may be omitted.

Blood for serum (for secondary research)

- If the samples can be processed and but not sent to the repository, the samples may be stored locally.
- If a BSL-3 environment is needed for processing these samples, these samples may be omitted.

8.1.3.2 Alternative Ordinal Scales

Given the limited clinical data available for COVID-19, the best construct of ordinal scale is not known. Additional data may be used to construct different ordinal scales to test their utility in a treatment study. These are hypothesis generating and will not be submitted as part of a final CSR.

8.2 Safety and Other Assessments

Study procedures are specified in the SOA. A study physician licensed to make medical diagnoses and listed on the 1572 will be responsible for all trial-related medical decisions.

Physical examination:

A targeted physical examination will be performed at baseline prior to initial infusion on Day 1. The baseline physical examination can be one that is conducted from screening to Day 1. Post-baseline physical examinations will be done only when needed to evaluate possible adverse event(s) (i.e. any new signs or symptoms). No routine physical exam is needed for study visits after Day 1.

Study staff at some sites are not allowed into the subject's rooms due to a limited supply of PPE and the need for strict respiratory isolation measures for COVID-19 patients. Because of limited access to subjects, physical exams can be performed by any licensed provider at the study hospital even if they are not study staff listed on the 1572. The study team can extract information from the hospital chart or EMR.

Clinical laboratory evaluations:

- Fasting is not required before collection of laboratory samples.
- Blood will be collected at the time points indicated in the SOA.
 - Clinical safety laboratory tests include WBC, differential, Hgb, PLT, creatinine, glucose, total bilirubin, AST, ALT, and PT. Sites that do not have access to a test for PT will be allowed to report an international normalized ratio (INR).
 - Day 1 clinical laboratory evaluations are drawn prior to initial infusion as a baseline and results do not need to be reviewed to determine if initial infusion should be given.
- Clinical laboratory testing will be performed at each clinical trial site in real time.

Table 3. Venipuncture Volumes¹

	Screen	Baseline						
Day +/- Window	-1 to 1	1 ± 1	3 ± 1	5 ± 1	8 ± 1	11 ± 1	15 ± 2	29 ± 3
Safety hematology, chemistry and liver tests	X 10mL ²	X 10mL ²	X 10mL ²	X 10mL ²	X 10mL ²	X 10mL ²	X ³ 10mL ²	X ³ 10mL ²
Blood for Serum		X 24mL	X 24mL	X 24mL	X 24mL	X 24mL	X 24mL	X 24mL
Plasma (includes PCR)		X 8mL	X 8mL	X 8mL	X 8mL	X 8mL		
Total volume	10mL	42ml	42mL	42ml	42ml	42ml	34mL	34mL
Total all study days								268~288 mL

1. See SOA in Section 1.2 for specific tests to be performed.

2. Total volume calculated assumes there are no routine clinical laboratory were done within 48 hours of screening that can be used for determining eligibility and no routine clinical laboratory tests were done within the window for that visitor 24 hours of Day 1, 3, 5, 8 and 11 and 48 hours for Day 15 and 72 hours for Day 29 if still hospitalized.

3. Safety laboratory tests will be collected on Day 15 and 29 if the subject is still hospitalized at these time points or if they return for an in-person outpatient visit and the site has the capacity to collect blood in the outpatient setting.

8.2.1 Procedures to be Followed in the Event of Abnormal Laboratory Test Values or Abnormal Clinical Findings

If a physiologic parameter (e.g., vital signs, or laboratory value) is outside of the protocol-specified range, then the measurement may be repeated once if, in the judgment of the investigator, the abnormality is the result of an acute, short-term, rapidly reversible condition or was an error. A physiologic parameter may also be repeated if there is a technical problem with the measurement caused by malfunctioning or an inappropriate measuring device (i.e., inappropriate-sized BP cuff).

